6.3 Populations for Analyses

The following subject populations will be considered in this trial:

- **All enrolled subjects:** All subjects who signed an informed consent form and were registered into the IVRS.
- **All treated subjects:** All subjects who received at least 1 dose of nivolumab.
- **Trial update analysis subjects:** All subjects who received at least 1 dose of nivolumab and 28 weeks have elapsed after the date of 1st dose
- **PK subjects:** All treated subjects with available serum time-concentration data.

- **Biomarker subjects:** All treated subjects with available biomarker data.

7 STATISTICAL ANALYSES

7.1 General Methods

Unless otherwise noted, the following subsections describe tabulations of discrete variables, by the frequency and proportion of subjects falling into each category, by tumor group. Percentages given in these tables will be rounded and, therefore, may not always sum to 100%. Percentages less than 0.1 will be indicated as ‘< 0.1’. Continuous variables will be summarized by tumor group using the mean, standard deviation, median, minimum and maximum values.

Time to event distribution will be estimated using Kaplan Meier techniques. This will be done for overall survival, duration of response and time to response. Median survival time along with 95% CI will be constructed based on a log-log transformed CI for the survivor function $S(t)$. Rates at fixed time points will be derived from the Kaplan Meier estimate and corresponding confidence interval will be derived based on Greenwood formula for variance derivation and on log-log transformation applied on the survivor function $S(t)$.

7.2 Study Conduct

Unless otherwise specified, the study conduct data will be presented on all treated subjects by tumor group.

7.2.1 Accrual

The following will be presented on the enrolled population

- Number of subjects accrued by country and investigational site
- Number of subjects accrued by month.

A by-subject listing of accrual by tumor type will be produced.

7.2.2 Relevant Protocol Deviations

The following programmable deviations from inclusion and exclusion criteria will be considered as relevant protocol deviations and be summarized on treated subjects. Non-programmable relevant eligibility and on-treatment protocol deviations, as well as significant (both programmable and non-programmable) eligibility and on-treatment protocol deviations will be reported through ClinSIGHT listings.

At Entrance:

- Subjects with baseline ECOG performance status > 1
- Subjects without measurable disease at baseline by CT or MRI per RECIST 1.1 criteria
- Subjects with screening laboratory values not meeting criteria listed in Target Population of Section 3.3.1 Inclusion Criteria of the study protocol
- Life expectancy < 16 weeks

- Subjects with target disease exclusions (listed in Target Disease Exclusions of Section 3.3.2 Exclusion Criteria of the study protocol)

On-study:

- Subjects receiving prohibited anti-cancer therapy (systemic therapy, radiotherapy, surgery) while on study therapy.
- Assessments not performed per protocol
- Study drug not administered as per protocol

A by subject listing of relevant protocol deviation will also be produced.

7.3 Study Population

Unless otherwise specified, the study population data will be presented on all treated subjects by tumor group.

7.3.1 Subject Disposition

Summary tables reflecting the number of subjects who are enrolled, who are treated and who completed the study will be presented by tumor type. The number of subjects who do not complete treatment phase part 1, treatment phase part 2 and follow-up, both overall and according to reasons for non-completion, will be summarized by tumor type.

A by subject listing of disposition will be provided.

7.3.2 Demographics and Baseline Characteristics

Descriptive statistics of the following baseline characteristics will be summarized by tumor group.

- Age
- Gender
- Race
- Ethnicity
- Smoking history: Never/Current/Former/Unknown
- Current Disease Diagnosis
 - Time from diagnosis to study treatment first dose
 - Stage: I/II/III/IV-Non-Metastatic/IV-Metastatic

7.3.3 Physical Measurements

Descriptive statistics of the following physical measurements will be summarized by tumor group.

- Baseline weight (kg)
- Body weight height (cm)
- Body mass index (BMI) (kg/m²)

- Baseline Eastern Cooperative Oncology Group (ECOG) performance status

Measurements will also be summarized by tumor group and study visit.

7.3.4 *Medical History*

General medical history will be coded and grouped into Preferred Terms (PT) by System Organ Class (SOC), using Medical Dictionary for Regulatory Activities (MedDRA) version 18.1 or higher. Listings and summaries will be based on the SOCs and PTs. Summaries will be provided by tumor group.

A by subject listing of disease specific medical history will be provided.

7.3.5 *Prior Therapy*

Descriptive statistics of prior therapies will be summarized for all treated subjects by tumor group.

- Prior Surgery Related to Cancer
 - Subjects with surgery (yes/no)
 - Time from surgery to study treatment first dose
- Prior Radiotherapy
 - Subjects with radiotherapy (yes/no)
 - Time from therapy stop to study treatment first dose
- Prior Systemic Cancer Therapy
 - Subjects with systemic cancer therapy (yes/no)
 - Setting of regimen (adjuvant therapy/metastatic disease/neo-adjuvant therapy)
 - Best response to regimen (CR/PR/SD/PD/unable to determine/not applicable)
 - Time from therapy stop to study treatment first dose

A by subject listing of the above prior therapies will be provided.

7.3.6 *Baseline Examinations*

Subjects with abnormal baseline physical examination will be tabulated by examination criteria and also by tumor type.

7.4 *Extent of Exposure*

Unless otherwise specified, the exposure data will be presented on treated subjects by tumor group.

7.4.1 *Administration of Study Therapy*

The following parameters will be summarized (descriptive statistics) by study therapy treatment phase:

- Relative dose intensity (%) using the following categories: < 50%; 50 - < 70%; 70 - < 90%; 90 - < 110%; ≥ 110%.
- Number of doses received (summary statistics)

- Cumulative dose
- Duration of treatment

A by-subject listing of extent of exposure: treatment phase, number of doses, date of first and last dose, cumulative dose, relative dose intensity, duration of treatment, and reason for discontinuation.

Table 7.4-1: Administration of Study Therapy: Definition of Parameters

nivolumab	
Dosing schedule per protocol	Phase 1: 240 mg Q2 weeks for 8 doses. Phase 2: 480 mg Q4 weeks until progression
Cumulative Dose	Cum dose (mg) is sum of the doses administered to a subject during the treatment period
Relative dose intensity (%)	Phase 1: [Cum dose (mg)/((Last dose date - Start dose date + 14) 240 / 14)] x 100 Phase 2: [Cum dose (mg)/((Last dose date - Start dose date + 28) x 480 / 28)] x 100
Duration of treatment	Last dose date - Start dose date +1

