6.2 Treatment Regimens

Treatment period, Phase 1: Subjects will receive treatment with nivolumab 240 mg as a 30 minute infusion on Day 1 of a treatment cycle every 2 weeks (14 days) for 8 doses until progression, unacceptable toxicity, withdrawal of consent, the study ends, or until Phase 2 dosing begins, whichever occurs first.

Treatment period, Phase 2: Beginning with Dose 9, subjects will receive nivolumab 480 mg as a 30 minute infusion every 4 weeks (\pm 3 days) until progression, unacceptable toxicity, withdrawal of consent, or the study ends, whichever occurs first. Subjects will receive study drug for the maximum treatment duration of 24 months.

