7.4.2 Modifications of Study Therapy

7.4.2.1 Dose Delays

Subjects should begin study treatment within 3 calendar days of treatment assignment. If required for clinic scheduling, subjects may be treated up to 3 days before or after the scheduled date, ie, at intervals of not less than 12 days from the previous dose during Q2W cycles. For Q4W dosing cycles, participants may be dosed within a ± 3 day window. A dose given more than 3 days after the intended dose date will be considered a delay. Subsequent treatments should be based on the actual date of administration of the previous dose of drug. A dose will be considered as actually delayed if the delay is exceeding 3 days after the intended dose date (i.e., greater than or equal to 4 days from scheduled dosing date). Length of dose delay is defined as (latter dose date – previous actual dose date - 14) for phase 1 and (latter dose date – previous actual dose date - 28) for phase 2. Dose delay may happen more than once. The phase 2 is beginning with dose 9 (2 weeks following the 8th dose). Dose delays will be divided into following categories: 4 - < 8 days, 8 - < 15 days, 15 - < 43, > 42 days. Reason for dose delay will be retrieved from CRF dosing pages.

The following parameters will be summarized:

- Number of dose delayed per subject, Length of Delay, and Reason for Dose Delay
- Number of subjects with at least one dose delayed along with reason for dose delay

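### Any time beyond the scheduled 14 days between dose 8 and dose 9 is counted in neither phase's relative dose intensity, so a hold at that point can still read as 100%

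*SAP*

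**What the plan says.** SAP Table 7.4-1 gives two RDI formulas. For the first eight doses it is "Phase 1: [Cum dose (mg)/((Last dose date - Start dose date + 14) 240 / 14)] x 100". From dose 9 it is "Phase 2: [Cum dose (mg)/((Last dose date - Start dose date + 28) x 480 / 28)] x 100". The schedule behind them is "Phase 1: 240 mg Q2 weeks for 8 doses. Phase 2: 480 mg Q4 weeks until progression".

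Section 7.4.1 sets the level of reporting: "The following parameters will be summarized (descriptive statistics) by study therapy treatment phase". It also sets the reporting bands: "Relative dose intensity (%) using the following categories: < 50%; 50 - < 70%; 70 - < 90%; 90 - < 110%; ≥ 110". No RDI for the whole course is defined.

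The same table defines cumulative dose as follows: "Cum dose (mg) is sum of the doses administered to a subject during the treatment period". It does not say whether the treatment period, the start date and the last date are those of one phase or of the whole course. SAP 6.2 uses the term separately for each phase, for example "Treatment period, Phase 2: Beginning with Dose 9, subjects will receive nivolumab 480 mg".

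On timing, SAP 7.4.2.1 says "The phase 2 is beginning with dose 9 (2 weeks following the 8th dose", so dose 9 is due 14 days after dose 8.

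**The concern.** RDI is meant to fall when treatment is given more slowly than planned. Here, whether it falls depends on where the hold occurs. A hold between two doses of the same phase lengthens that phase's denominator and lowers its RDI. A hold between dose 8 and dose 9 straddles the phases: Phase 1 has already been closed with a fixed 14 days, and Phase 2 does not open until dose 9 is given.

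At stake is the accuracy of one exposure parameter. Two subjects who lose the same treatment time can be reported in different RDI bands. Dose 9 is also the point where the regimen changes and where, under Protocol Table 5.1-2, the Week 16 scan must come first. The documents give no figure for how often dose 9 is held, so the number of subjects affected cannot be estimated.

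**Working it through.** The SAP states no RDI value, so there is none to reproduce. The check applies its formulas to a constructed dosing history.

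**Inputs**
- Doses 1 to 8: 240 mg on days 0, 14, ..., 98 (Table 7.4-1). Phase 1 total: 8 x 240 = 1,920 mg.
- Dose 9: due on day 112 (SAP 7.4.2.1). With a hold of h days it falls on day 112 + h.
- Later doses: 480 mg every 28 days. Six Phase 2 doses are assumed: 6 x 480 = 2,880 mg over 140 days from first to last.
- Dates and doses are taken per phase. The Phase 1 formula as extracted has no sign before 240; it is read as multiplication.

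**On schedule**
- Phase 1: 1,920 / ((98 + 14) x 240/14) = 1,920/1,920 = 100%.
- Phase 2: 2,880 / ((140 + 28) x 480/28) = 2,880/2,880 = 100%.
- Without the + 14, Phase 1 would read 1,920 / (98 x 240/14) = 1,920/1,680 = 114.3%. The + 14 therefore does count the scheduled 14 days between doses 8 and 9.

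**Hold of h days before dose 9, other doses on time**
- Phase 1 still runs from day 0 to day 98, plus 14: 100%.
- Phase 2 still spans 140 days from its own first dose, plus 28: 100%.
- h appears in neither formula, so the result is the same for any h.

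**The same 28-day hold elsewhere**
- Before dose 8: 1,920 / ((126 + 14) x 240/14) = 1,920/2,400 = 80.0% in Phase 1.
- Before dose 10: 2,880 / ((168 + 28) x 480/28) = 2,880/3,360 = 85.7% in Phase 2.
- Both fall in the 70 to below 90% band. The hold before dose 9 stays in the 90 to below 110% band.

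**Phase 1 closed at the dose 9 date**
- RDI = 1,920 / ((112 + h) x 240/14) = 112/(112 + h).
- h = 0: 100%. h = 14: 112/126 = 88.9%. h = 28: 112/140 = 80.0%.

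**Whole-course RDI, 8 + 6 doses**
- The two regimens have the same planned rate (240/14 = 480/28 mg per day), so RDI reduces to planned days over actual days. Planned days: 112 + 168 = 280.
- h = 14: 280/294 = 95.2%. h = 28: 280/308 = 90.9%.

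**Check on the phase-specific reading**
- With whole-course dates and doses, the Phase 2 formula gives 4,800 / ((252 + 28) x 480/28) = 4,800/4,800 = 100% on schedule, and it would count a hold before dose 9.
- The Phase 1 formula on the same inputs gives 4,800 / ((252 + 14) x 240/14) = 4,800/4,560 = 105.3% for a subject exactly on schedule. The pair of formulas is therefore coherent only when read by phase.

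**The case against.** **The interval is not left out.** A reader might infer that the whole time from dose 8 to dose 9 is missing from both denominators. It is not: the + 14 counts the scheduled 14 days. Only the excess is lost.

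**The reading is inferred.** Table 7.4-1 does not say that its dates and doses are phase-specific, and with whole-course inputs the Phase 2 formula would count the hold. This stands as a limit on the point. The by-phase summary, the wording of SAP 6.2 and the 105.3% result above all favour the phase-specific reading, but the SAP should say so.

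**The hold can be seen elsewhere.** A reader might infer that such holds are invisible and that exposure in general is overstated. The documents do not support either. SAP 7.4.2.1 summarises delayed doses with length and reason. Section 7.4.1 lists treatment phase with first and last dose dates, and section 7.4.2.2 lists drug administered. Number of doses and cumulative dose are unaffected. One weakness remains: section 7.4.2.1 subtracts 14 days for phase 1 and 28 for phase 2 without saying which applies to dose 9. Under the 28-day subtraction a 28-day hold would be recorded as 14 days and a 14-day hold as 0.

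**Large holds are exceptional.** Protocol 4.5.3 requires discontinuation when a delay exceeds 6 weeks from the previous dose, unless a listed exception applies. A 28-day hold puts dose 9 at exactly six weeks (14 + 28 = 42 days). Longer holds arise only under those exceptions, so they should not carry the argument.

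**Booking the excess to Phase 1 is a choice.** This is fair. Dose 9 is the first Phase 2 dose, and the SAP does not assign its lateness to Phase 1. On a whole-course RDI with 8 + 6 doses, 14- and 28-day holds give 95.2% and 90.9%, which stay in the same band as 100%. The change of band is therefore a feature of the by-phase figure. What does not depend on this choice is that the excess should be counted somewhere.

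**Conclusion.** The formulas in Table 7.4-1 are wrong as written for subjects whose dose 9 is late. On the phase-specific reading, time beyond the scheduled 14 days before dose 9 lowers neither RDI: both stay at 100% if the other doses are on time, against 80.0% in Phase 1 for the same 28-day hold one dose earlier.

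This rests on the phase-specific reading, which is well supported but not stated, and on histories in which only one dose is held. The effect is confined to the description of exposure. A reader might infer that the efficacy conclusions are affected; they are not, because neither the response-rate analysis nor the success and futility rules use RDI. It is a minor correction, worth making because it is so cheap.

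**What to change.** In SAP Table 7.4-1:
- State that start date, last date and cumulative dose are those of the phase concerned.
- For subjects who receive dose 9, set the Phase 1 denominator to (dose 9 date - start dose date) x 240/14.
- Keep the + 14 term only for subjects whose last dose is in Phase 1. Leave the Phase 2 formula unchanged.
- Optionally add a whole-course RDI: cumulative dose over both phases divided by the sum of the two phase denominators.

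The cost is a line or two in the table and the matching derivation code. On-schedule subjects stay at 100%; some other reported values become lower. No data collection and no clinical rule changes.

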7.4.2 Modifications of Study Therapy

7.4.2.1 Dose Delays

Subjects should begin study treatment within 3 calendar days of treatment assignment. If required for clinic scheduling, subjects may be treated up to 3 days before or after the scheduled date, ie, at intervals of not less than 12 days from the previous dose during Q2W cycles. For Q4W dosing cycles, participants may be dosed within a ± 3 day window. A dose given more than 3 days after the intended dose date will be considered a delay. Subsequent treatments should be based on the actual date of administration of the previous dose of drug. A dose will be considered as actually delayed if the delay is exceeding 3 days after the intended dose date (i.e., greater than or equal to 4 days from scheduled dosing date). Length of dose delay is defined as (latter dose date – previous actual dose date - 14) for phase 1 and (latter dose date – previous actual dose date - 28) for phase 2. Dose delay may happen more than once. The phase 2 is beginning with dose 9 (2 weeks following the 8th dose). Dose delays will be divided into following categories: 4 - < 8 days, 8 - < 15 days, 15 - < 43, > 42 days. Reason for dose delay will be retrieved from CRF dosing pages.

The following parameters will be summarized:

- Number of dose delayed per subject, Length of Delay, and Reason for Dose Delay
- Number of subjects with at least one dose delayed along with reason for dose delay

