#### **4.5 Selection and Timing of Dose for Each Subject**

Subjects will receive treatment with nivolumab 240 mg as a 30 minute IV infusion on Day 1 of a treatment cycle every 2 weeks (14 days) for 8 doses until progression, unacceptable toxicity, withdrawal of consent, the study ends, or until Q4W dosing begins, whichever occurs first. Participants should begin study treatment within 3 calendar days of treatment assignment. Beginning with dose 9 (2 weeks following the 8th dose), subjects will receive treatment with nivolumab 480 mg as a 30 minute IV infusion every 4 weeks (28 days) ( $\pm$  3 days) until progression, unacceptable toxicity, withdrawal of consent, maximum of 24 months of treatment, or the study ends, whichever occurs first.

If required for clinic scheduling, subjects may be treated up to 3 days before or after the scheduled date, ie, at intervals of not less than 12 days from the previous dose during Q2W cycles. For Q4W dosing cycles, participants may be dosed within a  $\pm$ 3 day window. A dose given more than 3 days after the intended dose date will be considered a delay. Subsequent treatments should be based on the actual date of administration of the previous dose of drug.

No dose escalations or reductions of nivolumab are allowed. Dosing visits are not skipped, only delayed.

There are no premedications recommended for nivolumab until infusion reactions have been observed in the subject. Subjects should be carefully monitored for infusion reactions during nivolumab administration. If an acute infusion reaction is noted, subjects should be managed according to [Section 4.5.6](#).

Dose delay criteria, criteria to resume treatment, and treatment discontinuation criteria can be found in Section 4.5.1, [Section 4.5.2](#), and [Section 4.5.3](#), respectively.

Nivolumab infusions are compatible with polyvinyl chloride (PVC) or polyolefin containers and infusion sets, and glass bottles.

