2 STUDY DESCRIPTION

2.1 Study Design

This is an open-label, multicenter, phase 2 study of nivolumab monotherapy in adult (≥ 18 years) subjects with advanced malignancies not previously evaluated with nivolumab or other I/O agent. Subjects must have received previous standard-of-care therapies (for primary therapy or post primary therapy).

The study design schematic is presented in Figure 1.

Figure 1: Study Design Schematic

- a. Tumor tissue will be evaluated for sufficient tumor that meet the minimum quality requirements, received by a central laboratory before first treatment
- b. Blood sample will be collected at screening or before first nivolumab administration
- c. Subjects will be treated until confirmed progression or unacceptable toxicity, or 24 months of treatment
- d. Time interval between dose 8 and dose 9 is 2 weeks; time interval between dose 9 and dose 10 is 4 weeks

Enrollment of up to 350 subjects is expected to require approximately 24 months. Interim monitoring and final analyses are planned. Subjects will receive study drug for the maximum treatment duration of 24 months.

The start of the trial is defined as first visit for first subject screened. End of trial is defined as the last scheduled procedure shown in the Time & Events Schedule for the last subject. Study completion is defined as the final date on which data for the primary endpoint was or is expected to be collected, if this is not the same.

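### The SAP's dose-delay formula subtracts 28 days at dose 9, which is due 14 days after dose 8, so dose-9 delays are measured 14 days too short and many are misfiled or fit no category

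*SAP*

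**What the plan says.** SAP 7.4.2.1 gives one formula per treatment phase. For the first: "Length of dose delay is defined as (latter dose date – previous actual dose date - 14) for phase 1". For the second: "latter dose date – previous actual dose date - 28) for phase 2". Shortly afterwards the paragraph states: "The phase 2 is beginning with dose 9 (2 weeks following the 8th dose".

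The rest of the plan agrees on both the phase and the due date of dose 9:

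- SAP 6.2 puts dose 9 in the second phase: "Treatment period, Phase 2: Beginning with Dose 9, subjects will receive nivolumab 480 mg".
- SAP 2.1, note d to the schematic, gives the intervals: "Time interval between dose 8 and dose 9 is 2 weeks; time interval between dose 9 and dose 10 is 4 weeks".
- Protocol 4.5 gives the same schedule: "Beginning with dose 9 (2 weeks following the 8th dose), subjects will receive treatment with nivolumab 480 mg".

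SAP 7.4.2.1 also says when a dose counts as delayed: when it is more than 3 days past its intended date, which the SAP restates as "i.e., greater than or equal to 4 days from scheduled dosing date". Delays are sorted into four categories: 4 to <8, 8 to <15, 15 to <43 and >42 days. The planned summaries are the number of delayed doses per subject with length and reason, and the number of subjects with at least one delayed dose.

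**The concern.** The subtraction depends on the phase, but the scheduled gap does not change where the phase changes. Phase 2 starts at dose 9, while the first 28-day gap runs from dose 9 to dose 10. Read literally, the formula takes 28 days off a gap that should be 14.

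This sets two rules in one paragraph against each other. A dose 9 given 10 days late is a delay by the intended-date rule, yet its computed length is -4 days. The dose in question is the one at which the regimen changes, and the error always runs in the same direction, towards shorter delays. At stake is the accuracy of a planned descriptive exposure summary.

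**Working it through.** **Inputs**

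- Phase 1 length: gap - 14. Phase 2 length: gap - 28 (SAP 7.4.2.1).
- Dose 9 is in phase 2 (SAP 6.2 and 7.4.2.1).
- Dose 9 is due 14 days after dose 8 (SAP 2.1 and 7.4.2.1; Protocol 4.5).
- A delay is 4 days or more. The categories are 4 to <8, 8 to <15, 15 to <43 and >42 days (SAP 7.4.2.1).

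The documents give no figure that depends on this formula, so there is none to reproduce.

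**Step 1: does the formula return 0 for an on-time dose?**

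- Doses 2 to 8: 14 - 14 = 0.
- Dose 9: 14 - 28 = -14.
- Dose 10 onward: 28 - 28 = 0.

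Only dose 9 fails.

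**Step 2: size of the error.** Let t be the true delay of dose 9 in days. The gap since dose 8 is 14 + t, so the computed length is (14 + t) - 28 = t - 14. The length is 14 days short for every value of t.

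**Step 3: effect on the categories**

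| True delay t (days) | Computed length t - 14 | Correct category | Category under the formula |
|---|---|---|---|
| 4 to 7 | -10 to -7 | 4 to <8 | none |
| 8 to 14 | -6 to 0 | 8 to <15 | none |
| 15 to 17 | 1 to 3 | 15 to <43 | none |
| 18 to 21 | 4 to 7 | 15 to <43 | 4 to <8 |
| 22 to 28 | 8 to 14 | 15 to <43 | 8 to <15 |
| 29 to 42 | 15 to 28 | 15 to <43 | 15 to <43 (correct) |
| 43 to 56 | 29 to 42 | >42 | 15 to <43 |
| 57 or more | 43 or more | >42 | >42 (correct) |

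The 14 whole-day values from 4 to 17 have no category. The first delay to reach the 4-day threshold is a true 18 days, which is 14 + 18 = 32 days after dose 8, and it is scored as 4.

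**Step 4: which of these delays are the ordinary ones?** Protocol 4.5.3 requires discontinuation, with listed exceptions, when a delay exceeds 6 weeks from the previous dose. For dose 9, a 42-day gap is a true delay of 42 - 14 = 28 days. Dose-9 delays that need no such exception therefore run from 4 to 28 days. All 25 of these values are either uncategorised (4 to 17) or misfiled (18 to 28).

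**Step 5: check of the correction.** With 14 days subtracted at dose 9, the length is (14 + t) - 14 = t. Every value of t from -3 to 99 was checked, and each falls where it should.

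**The case against.** The strongest objection is that the SAP decides whether a dose is delayed separately from how long the delay is. The delay rule refers to the intended date, not to the subtraction, and the paragraph gives the intended date of dose 9. On that reading a dose 9 that is 4 to 17 days late still enters the counts, and its reason still comes from the case report form. This stands. A reader might infer that such delays are never counted, but the text does not say that. They leave the counts only if the flag is programmed from the length formula. If it is not, the dose is flagged as delayed with a length of -10 to 3 days and no category, which is still an inconsistent output.

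A second objection is that the remark on the 2-week interval, placed just after the formulas, can be read as qualifying them. The phase 1 relative dose intensity in Table 7.4-1 also adds 14 days after the last phase 1 dose, which suggests that the gap between doses 8 and 9 belongs to phase 1. A programmer might well proceed that way. But the remark gives a due date without changing the subtraction, the same sentence puts dose 9 in phase 2, and dose intensity is a different quantity with its own formula. Nothing written exempts dose 9.

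Third, the effect is small. It touches one interval per subject in a descriptive table. A length of -14 for each on-time dose 9 would probably be noticed in programming checks, and the Data Presentation Plan, which is not available here, might settle the matter. The limited size stands. The likelihood that someone notices is not a reason to leave the rule as written.

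**Conclusion.** The length rule is wrong as written for dose 9: it understates the delay by exactly 14 days. True delays of 4 to 17 days fit no category, and those of 18 to 28 and 43 to 56 days are filed too short. This rests on the literal reading that a phase 2 dose takes the phase 2 formula.

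Two broader conclusions are tempting, and the documents do not support them.

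- A reader might infer that every subject who receives dose 9 is affected. An on-time dose 9 scores -14 instead of 0, but both are below the threshold, so no delay count or category changes. These change only for subjects whose dose 9 is at least 4 days late, and the documents do not allow that number to be estimated.
- A reader might infer that every delay still counted lands in too short a category. Delays of 29 to 42 days and of 57 days or more stay in the right one, with only the length wrong.

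The consequence is confined to the dose-delay summary. The response rate, the other efficacy endpoints and the Bayesian decision rules do not use this quantity. The correction is worth making because it is cheap and the output is planned, not because any conclusion about efficacy depends on it.

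**What to change.** In SAP 7.4.2.1, replace the two phase-specific formulas with one: length of delay equals the dose date, minus the previous actual dose date, minus the scheduled interval. Set the scheduled interval to 14 days for doses 2 to 9 and 28 days from dose 10 on, as the documents already schedule. State that the delay flag (4 days or more) is derived from this same quantity, so that flag, length and category cannot disagree.

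The cost is one sentence in the SAP and about one line of derivation code. This is a change to an analysis derivation only and alters nothing in the dosing schedule.
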